3.4 Definitions of Study Variables

Recurrent VTE

1. Pulmonary embolism
 - a (new) intraluminal filling defect in segmental or more proximal branches on CT,
 - a (new) intraluminal filling defect or an extension of an existing defect or a new sudden cutoff of vessels more than 2.5 mm in diameter on the pulmonary angiogram,
 - a (new) perfusion defect of at least 75% of a segment with a local normal ventilation result (high-probability) on ventilation/perfusion lung scintigraphy.

- inconclusive CT, Pulmonary Angiography, or lung ventilation/perfusion scintigraphy with demonstration of DVT in the lower extremities by compression ultrasound or venography (Recurrent PE is not diagnosed by CT or ventilation/perfusion scans showing unchanged filling defects compared with the study qualifying images):

OR

2. Suspected (recurrent) DVT with one of the following findings if there were no previous DVT investigations:
 - abnormal compression of a deep vein, including calf, gastrocnemius, saphenous vein, femoral, brachial, axillary or jugular veins on ultrasound
 - an intraluminal filling defect on venography:

OR

3. Suspected (recurrent) DVT with one of the following findings if there was a DVT investigation at screening:
 - abnormal compression ultrasound where compression had been normal or, if non-compressible during screening, a substantial increase (4 mm or more) in diameter of the thrombus during full compression,
 - proximal extension of an intraluminal filling defect, or a new intraluminal filling defect, or proximal extension of non-visualization of veins in the presence of a sudden cut-off on venography

(Recurrent DVT is not diagnosed with compression abnormalities in the same vein as was abnormal on the study qualifying ultrasound).

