2 OBJECTIVES

2.1 Primary Objectives

Evaluate the primary effectiveness of an implementation protocol to identify and manage care of patients diagnosed with DVT and/or PE who are discharged from the ED and treated with apixaban. Treatment failure rate, defined as the numerator, comprising the sum of subjects treated in this protocol who are re-hospitalized for >24 hours within 30 days of enrollment for either objectively diagnosed VTE or for major or clinical relevant non-major bleeding related event, divided by the denominator of enrolled subjects. Protocol success will be defined by the upper limit 95% CI for this proportion < 2.0%.

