3.2.1 Inclusion Criteria

Criteria for initial VTE diagnosis require a filling defect interpreted as positive on computerized tomographic pulmonary angiography, a ventilation-perfusion lung scan interpreted as high probability, or an incompressible vein observed on venous ultrasound of an extremity or jugular vein. Screening includes electronic surveillance of the “VTE home treatment order set” which ensures low risk criteria and then provides appropriate medication, including apixaban as an option, and discharge instructions. Enrollment occurs at the time of written informed consent.

1. Patients must be **low risk**, as defined by either A or B below:

A. The modified Hestia criteria:

- Systolic blood pressure > 100 mm Hg
- No thrombolysis needed
- No active bleeding
- SaO₂ >94% while breathing room air
- Not already anticoagulated
- No more than two doses of IV narcotics in the emergency department
- Other medical or social reasons to admit
- Creatinine clearance >30mL/min
- Not pregnant, severe liver disease or heparin induced thrombocytopenia

OR

B. The physician opinion that a patients' overall social and medical situation is favorable for home treatment and the patient has a zero score on the simplified pulmonary embolism severity index (sPESI).

All of the following must true:

- Age < 81 years
- No history of cancer
- No history of heart failure or chronic lung disease
- Pulse < 110 beats/min
- SBP > 99 mm Hg
- O₂ sat >89%

We have chosen either criteria because both have been found equal in terms of safety for outpatient treatment of PE.^{6,22} Hestia includes implicit questions that most emergency physicians would use as criteria for discharge (e.g., overall medical status and social situation), whereas sPESI does not. For that reason, we have added the additional gestalt assessment question about physician discretion.

[figure not shown]
2. Patients must be discharged in <24 hours after triage in an ED visit with diagnosis of VTE using objective criteria in the emergency department.

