3.3 Data Source/Data Collection Process

The figure below demonstrates the data flow process. Each site will complete an electronic case report form that will be linked by a study ID (e.g. CMC001) to the study site enrollment registry, maintained at the study site. The study deliverable is a PHI deidentified REDCap data set (appendix). Placards will be posted in the emergency department with a flow diagram similar to the one diagrammed above. Each site will create a specific “VTE home treatment” order set which prints prescriptions. Subjects will follow-up in designated anticoagulation centers or with a primary care physician. The duration of anticoagulation will usually be at least 3 months.(16) Patients will be identified by query of the electronic order set. Outcomes will be assessed by medical record review and/or a telephone call to each patient made after 30 days after discharge from the emergency department to document outcomes from the time of discharge to 30 days thereafter.

The primary efficacy and safety aims will be assessed by telephone survey and medical record review at or after 30 days, asking the subject explicitly about any change in health status, any unscheduled visit to an emergency department or other healthcare provider, re-hospitalizations, VTE diagnoses, or bleeding events. The script and procedures for the phone call, including handling disconnected numbers, and non-answers will be in the guidance document.

Definitions of recurrent VTE: Study personnel will perform a chart review to confirm suspected recurrent PE/DVT, which will require explicit radiographic or ultrasonic evidence of PE/DVT.

The definition of **re-hospitalization for bleeding** requires chart review demonstrating explicit written decision-making by the admitting emergency physician that a patient was admitted (requiring >24 hour stay) for medical or procedural care to manage objective or suspected bleeding. This would include charted evidence of initially suspected but later disproven bleeding such as gastrointestinal bleeding. Bleeding events will be further characterized as **major bleeding or clinically relevant non-major bleeding**, using published criteria, further defined in the guidance document and using previously established criteria.^{3,21}

Secondary objectives

Discontinuation of apixaban. During the follow-up telephone call, patients will be asked if they discontinued apixaban and if so, what anticoagulant they are currently taking.

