3.4.1 Outcomes/Endpoint Variables

The primary outcome measures the frequency of one or more episodes of a subject returning for medical care resulting in hospital stay > 24 hours as a direct result of either recurrent VTE or major or clinical relevant non-major bleeding within 30 days of VTE diagnosis that initiated enrollment. For the purpose of this protocol, these events are synonymous with the term treatment failure endpoints. Each case requires medical documentation indicating the reason for hospitalization was for treatment, diagnosis or monitoring of the recurrent VTE or bleeding condition. For example, if a subject returns to an emergency department for chest pain, and reports a nosebleed on the same day, and is hospitalized for testing related to the chest pain, and is not found to have recurrent VTE, the subject does not meet a primary failure endpoint. However, if the subject were admitted for nose packing, or was discovered to have a new PE, then in either case, the subject would meet the primary failure endpoint.

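### In Section 3.4, growth of 4 mm or more in the qualifying vein counts as recurrent DVT under item 3 but is excluded by the closing note, so one limb of a primary-endpoint component needs reconciling

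*Protocol*

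**What the plan says.** Section 3.4 of the Protocol defines recurrent VTE in three items. Item 3 covers suspected recurrent DVT in patients who had a DVT investigation at screening. Its ultrasound criterion has two limbs:

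- (a) abnormal compression where compression had been normal;
- (b) "if non-compressible during screening, a substantial increase (4 mm or more) in diameter of the thrombus during full compression".

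The item closes with a note: "Recurrent DVT is not diagnosed with compression abnormalities in the same vein as was abnormal on the study qualifying ultrasound". The matching note for PE in item 1 is narrower: "Recurrent PE is not diagnosed by CT or ventilation/perfusion scans showing unchanged filling defects compared with the study qualifying images".

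One route into the study (Section 3.2.1) is "an incompressible vein observed on venous ultrasound of an extremity or jugular vein". The primary outcome (Section 3.4.1) is a hospital stay of more than 24 hours "as a direct result of either recurrent VTE or major or clinical relevant non-major bleeding within 30 days of VTE diagnosis". Success requires the upper 95% limit for the failure proportion to lie below 2.0% (Sections 2.1 and 4.1.1), using the exact binomial interval.

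**The concern.** Limb (b) can only describe a vein that was already abnormal at screening. If the screening ultrasound was also the qualifying one, this is the vein that the note takes out of consideration. A patient readmitted with clear growth of the index clot is then a recurrence under limb (b) and not a recurrence under the note.

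This affects one part of the primary numerator. Following the note literally drops same-vein progression during follow-up and pushes the result towards success. Following limb (b) keeps it. Section 3.3 leaves confirmation to study personnel by chart review, so two sites could classify the same scan differently. If the rule is settled only after events are known, the choice is open to the suspicion that it followed the result.

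**Working it through.** **1. The texts side by side**

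| Finding on repeat imaging, DVT qualified by ultrasound | Item 3 criteria | Closing note |
|---|---|---|
| Newly abnormal compression in a different vein | recurrence, limb (a) | silent |
| Qualifying vein still abnormal, growth below 4 mm | not a recurrence on ultrasound | not a recurrence |
| Qualifying vein, growth of 4 mm or more | recurrence, limb (b) | not a recurrence |
| Proximal extension or new defect on venography | recurrence | silent (it concerns compression) |

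Only the third row conflicts. Item 2 (no earlier DVT investigation) and the PE criteria are outside the note.

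**2. Is there a tie-breaker?** The PE note is confined to "unchanged filling defects compared with the study qualifying images"; the DVT note has no such limit. Section 3.3 asks for imaging evidence, "which will require explicit radiographic or ultrasonic evidence of PE/DVT", which does not settle the same-vein case. Section 3.3 cites the guidance document for telephone procedures and bleeding criteria, not for recurrent DVT. No sentence gives limb (b) or the note precedence.

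**3. What one reclassified case does to the result**

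Inputs: N = 850 (Section 4.2); exact binomial 95% interval (Section 4.1.1), taken as two-sided; threshold 2.0% (Section 2.1); planning scenario of 3 VTE recurrences plus 3 major haemorrhages (Section 4.2).

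Formula: the upper limit for x failures is the 0.975 quantile of Beta(x+1, 850−x). Equivalently, it is the p at which P(X ≤ x) = 0.025.

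The plan's own figure first: 6 failures gives 1.530%, against 1.5 in the Section 4.2 table, so it reproduces.

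| Failures | Exact upper limit |
|---|---|
| 3 | 1.028% |
| 6 | 1.530% |
| 7 | 1.689% |
| 8 | 1.846% |
| 9 | 2.0004% |
| 10 | 2.153% |

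At p = 0.02, P(X ≤ 8) = 0.01196, below 0.025, so 8 failures succeeds. P(X ≤ 9) = 0.02505, just above 0.025, so 9 does not strictly succeed. Moving from 8 to 9 adds 2.0004 − 1.846 = 0.154 percentage points.

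The Section 4.2 table prints 1.9 for 9 failures and 2.0 for 10, which the exact two-sided method does not reproduce. A reader using the printed table would place the boundary one failure higher. That is a separate matter.

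**4. The planning scenario.** Assume that between 0 and 3 of the 3 planned recurrences are same-vein cases. The total then ranges from 3 + 0 = 3 to 3 + 3 = 6 failures, and the upper limit from 1.028% to 1.530%. Both are below 2.0%. If same-vein cases instead came on top of the 6, it would take three of them (6 + 3 = 9) to lose success.

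**The case against.** The best defence is that the two sentences can be reconciled. The note speaks of compression abnormalities, whereas limb (b) requires a measured increase in diameter. A sensible reader would take the note to mean that persisting non-compressibility alone is not recurrence, since limb (b) would otherwise do little. This is plausible and may be what was intended. But it needs a qualifier that the DVT note lacks and the PE note has, so a site may also take the absence as deliberate.

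The conflict is also narrower than it first looks. Limb (b) turns on a screening investigation and the note on the qualifying ultrasound. A patient who qualified by CT or lung scan and also had a screening ultrasound may fall under limb (b) without touching the note. So limb (b) is not wholly cancelled, and the numerator as a whole is not undecidable.

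A further case against weight is rarity. An affected patient needs growth of 4 mm or more in the qualifying vein, no other qualifying finding, and a stay of more than 24 hours because of it, all within 30 days. This stands, and it limits the severity.

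A reader might also infer an opposite error: that Section 3.3, which asks only for imaging evidence, and Sections 2.1 and 4.1.1, which count readmission "for either objectively diagnosed VTE or for major or clinical relevant non-major bleeding related event", would let an unchanged index clot count as a failure. The documents do not support that. Sections 1.2, 3.4.1, 4.1 and the success sentence of 4.1.1 all refer to recurrent VTE or recurrence. Section 3.3 itself speaks of confirming suspected recurrence, and Section 3.4 rules out unchanged PE defects and persisting same-vein abnormalities. The wording in 2.1 and 4.1.1 is loose shorthand.

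**Conclusion.** The point holds in a limited form. For patients who qualified by ultrasound, growth of 4 mm or more in the qualifying vein is included by limb (b) of item 3 and excluded by the closing note, and the protocol does not say which governs. The literal note favours success.

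The effect cannot be sized, because the protocol gives neither the share of patients who qualify by ultrasound nor an expected number of same-vein progressions. One such case alters the verdict only when the total is at 8 or 9 failures; in the planning scenario it does not. It would go too far to say that this ambiguity is likely to decide the study.

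Severity is moderate to minor: a real inconsistency in a primary-endpoint component, with a small probable effect. The figures assume a two-sided exact interval and the full denominator of 850.

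**What to change.** Reconcile the two sentences in Section 3.4 before any event is classified. One way is to limit the DVT note, as the PE note is limited, so that it excludes only those abnormalities in the qualifying vein that do not meet the item 3 growth criterion. If the sponsor intends the note to prevail, limb (b) should be restricted to match. Either way, one scan must give one answer.

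As optional tidying, Sections 2.1, 3.3 and 4.1.1 could refer to recurrent VTE as defined in Section 3.4.

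The cost is one sentence in a protocol amendment, plus the optional cross-references, and a note to sites. No new data are needed and patient care does not change.

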3.4.1 Outcomes/Endpoint Variables

The primary outcome measures the frequency of one or more episodes of a subject returning for medical care resulting in hospital stay > 24 hours as a direct result of either recurrent VTE or major or clinical relevant non-major bleeding within 30 days of VTE diagnosis that initiated enrollment. For the purpose of this protocol, these events are synonymous with the term treatment failure endpoints. Each case requires medical documentation indicating the reason for hospitalization was for treatment, diagnosis or monitoring of the recurrent VTE or bleeding condition. For example, if a subject returns to an emergency department for chest pain, and reports a nosebleed on the same day, and is hospitalized for testing related to the chest pain, and is not found to have recurrent VTE, the subject does not meet a primary failure endpoint. However, if the subject were admitted for nose packing, or was discovered to have a new PE, then in either case, the subject would meet the primary failure endpoint.

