1 INTRODUCTION

1.1 Study Rationale

This work seeks to generalize a protocol to improve the transition of care of patients with venous thromboembolism (VTE, including both deep vein thrombosis, DVT, and pulmonary embolism, PE) from the emergency department (ED) to home treatment. We hypothesize a <2% rate of 30 day re-hospitalization for recurrent VTE or bleeding in patients selected as low risk by the modified Hestia criteria or physician discretion and sPESI negative. The 2% upper limit of the 95% CI threshold is justified based upon data from AMPLIFY and pooled data from EINSTEIN DVT and PE which show a point estimate 30 day VTE recurrence rate of 1-1.2%.^{1,2} For patients deemed low risk in the present study, it can reasonably be predicted this rate will be considerably lower. The 30 day incidence of major bleeding were <1.0% in both AMPLIFY and EINSTEIN, and for patients with low risk of bleeding, the rate can be expected to be about 0.5% with upper limit 95% CI <1.0%.³ Additionally, the 90 day incidence of the composite rate for VTE recurrence and major bleeding reported in systematic reviews and meta analyses of outcomes of low risk VTE patients diagnosed in the ED and treated at home with vitamin K antagonists (VKAs) was 18/785 (2.2%, 95% CI 1.4-3.6%).^{4,5} Den exer et al randomized 275 Hestia negative patients to be treated with VKAs at home; 90 day follow up found 3 with recurrent VTE and 3 with major bleeding (6/275, 2.2%).⁶ Taken together, we submit these data which support the assertion of the upper limit 30 day failure rate (composite of VTE recurrence and bleeding) <2.0% to constitute a reasonable and prudent expectation of standard care. Recent evidence indicates the safety and acceptance of home treatment of both DVT and PE.^{7,8} Patient interviews indicate a strong patient preference to this approach over use of injectable low molecular weight heparin and vitamin K antagonists (e.g., <https://iu.box.com/riva-patient-interviews>). However, clinicians remain reluctant to discharge DVT and PE patients because lack of a “hard wired” system to guarantee patient follow-up⁹. **To help facilitate this transition in care**, in 2013 in Indianapolis, the project leader/principal investigator, implemented an outpatient treatment protocol using target specific anticoagulants (TSA) for patients with VTE in two hospitals with a low risk of treatment failure and drug related side effects. Most importantly, this included two dedicated clinics (known locally as the KLOT clinics) for these patients to follow-up. Two manuscripts describing the outcomes of the first 106 subjects, as well as a case-control cost effectiveness study have been published.^{10,11} A third paper documented good patient outcomes and quality of life equal to patients treated with usual care.⁹ With more experience, we have found the transition of care can occur from the ED to primary care physicians and even to existing anticoagulation clinics.

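### A death from PE or bleeding without a hospital stay of more than 24 hours counts as a non-failure in the primary endpoint and so favours meeting the <2.0% success rule

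*Protocol*

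**What the plan says.** Protocol 2.1 counts as a treatment failure a subject "re-hospitalized for >24 hours within 30 days of enrollment for either objectively diagnosed VTE", or for major or clinically relevant non-major bleeding. Section 4.1.1 repeats this. Both divide by enrolled subjects, and success is an upper 95% limit below 2.0%.

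Section 3.4.1 gives the same event as "a subject returning for medical care resulting in hospital stay > 24 hours as a direct result of either recurrent VTE" or such bleeding, and adds that "these events are synonymous with the term treatment failure endpoints". It then sets a condition for every case: "Each case requires medical documentation indicating the reason for hospitalization was for treatment, diagnosis or monitoring of the recurrent VTE or bleeding condition".

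Section 3.3 fixes the two components. Re-hospitalization for bleeding needs a charted decision that the patient "was admitted (requiring >24 hour stay) for medical or procedural care to manage objective or suspected bleeding". It includes bleeding that was suspected on admission and later ruled out. Suspected recurrent VTE is confirmed by chart review, "which will require explicit radiographic or ultrasonic evidence of PE/DVT". The recurrent-VTE definitions in 3.4 rest on imaging and have no category for fatal PE.

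Death is named in none of the primary, secondary or exploratory objectives (2.1 to 2.3) and nowhere in section 4. It appears in section 6, as a criterion for a serious adverse event and in a general example about endpoint components.

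**The concern.** The endpoint is meant to show whether sending low-risk VTE patients home works. Its gravest failures are sudden fatal PE and fatal bleeding, and these are the events most likely to end before a 24-hour stay has accrued. Under the stated definition they are scored like an uneventful course. An admission of more than 24 hours for bleeding that is later disproven, in contrast, falls within the section 3.3 definition of re-hospitalization for bleeding.

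The secondary objectives do not fill the gap. The only clinical event counted in 2.2 is subject-reported non-major bleeding. A confirmed recurrent VTE or major bleed with a stay of 24 hours or less is in neither the primary nor a secondary count. The success claim could therefore be met while fatal treatment failures are missing from the figure it rests on.

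**Working it through.** **How the definition classifies events within 30 days**

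| Event | In denominator | In numerator |
|---|---|---|
| Fatal PE or bleed at home | yes | no: no hospitalization |
| Fatal PE or bleed in the ED or within 24 h of return | yes | no: stay not >24 h |
| Death after a stay >24 h for recurrent VTE or qualifying bleeding | yes | yes, through the stay |
| Confirmed recurrent VTE or major bleed, stay not >24 h | yes | no |

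**Inputs.** N = 850 (4.2). Exact binomial 95% interval (4.1.1); its sidedness is not stated, so two-sided is assumed. Criterion: upper limit < 2.0% (2.1, 4.1.1). Planning scenario: 3 VTE recurrences + 3 major hemorrhages = 6 failures (4.2). The number of uncounted deaths is not in the protocol; 0 to 3 is an assumed range.

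**Formula.** For x failures in n subjects, the two-sided exact upper limit is U(x) = the 0.975 quantile of Beta(x + 1, n − x).

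**Reproducing the plan's figure.** U(6) = 0.975 quantile of Beta(7, 844) = 1.53%. The table in 4.2 prints 1.5 for 6 failures, so the planning figure is reproduced.

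**Limits near the boundary**

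| x | U(x) | < 2.0%? |
|---|---|---|
| 6 | 1.530% | yes |
| 7 | 1.689% | yes |
| 8 | 1.846% | yes |
| 9 | 2.0004% | no |
| 10 | 2.153% | no |

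Eight is the largest count that meets the criterion. One more event adds about 0.15 to 0.16 percentage points here (1.846 − 1.689 = 0.157; 2.0004 − 1.846 = 0.154).

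**Effect of counting the deaths**

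| Hospitalized failures | Deaths without a qualifying stay (assumed) | Limit as the protocol counts | Limit with deaths counted |
|---|---|---|---|
| 6 | 1 | 1.53%, met | 1.69%, met |
| 6 | 2 | 1.53%, met | 1.85%, met |
| 6 | 3 | 1.53%, met | 2.0004%, not met |
| 8 | 1 | 1.85%, met | 2.0004%, not met |

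**Sensitivity.** The table in 4.2 prints 1.9 for 9 failures and 2.0 for 10, which the two-sided exact formula does not give (2.0004 and 2.153). Taken as printed, the last count below 2.0 would be 9. With a one-sided 95% exact limit it would be 10 (1.987%; 11 gives 2.133%). Either choice moves the boundary up by one or two events. Neither changes how a death is classified.

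**The case against.** The strongest reply is that re-hospitalization is the declared target. The synopsis speaks of a readmission rate, 1.1 names return to the hospital as the deliverable, and the research question in 1.2 is about events requiring re-hospitalization. This is a descriptive single-arm registry, and deaths are not hidden: they are serious adverse events (6.1), must be collected (6.2.1) and are reported in aggregate (6.2). Discontinuation for bleeding or recurrence is also recorded as an exploratory item (2.3). All of this is true, but none of it puts a death into the numerator on which success is judged, and the protocol itself labels that numerator treatment failure. Ascertainment is also weak for this event: the chart review for adverse events in 3.3 is triggered by the subject's own day-30 answer, which a deceased subject cannot give.

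The example closing 3.4.1, in which a newly found PE meets the endpoint, might seem to waive the stay condition. It continues the case of a hospitalized subject, and the section still demands a documented reason for hospitalization.

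Three stronger readings are tempting and are not supported:

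- *Short-stay recurrences are excluded by design.* A reader might infer this from "Patients must be discharged in <24 hours after triage in an ED visit with diagnosis of VTE" in 3.2.1. That rule concerns the index visit only. The modified Hestia list requires that the patient is not already anticoagulated, and 3.2.2 excludes VTE diagnosed on anticoagulants taken as prescribed, so a recurrence on treatment lies outside the home pathway. The protocol gives no frequency for short-stay recurrences.
- *The 2% limit is easier to meet than its benchmark.* Section 1.1 supports the limit with trials that "show a point estimate 30 day VTE recurrence rate of 1-1.2" per cent and with major-bleeding rates, none described with a stay condition. The endpoint is narrower in that respect. It is also broader, because it adds clinically relevant non-major bleeding, and 3.3 admits bleeding later disproven. The net direction is not shown.
- *Such a death is a protocol success.* Success is a study-level result. The individual death is a non-failure, which favours that result.

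**Conclusion.** The point holds. As the protocol defines treatment failure, a death from PE or bleeding without a stay of more than 24 hours is a non-failure, and every such death lowers the observed rate. The classification follows from the text and needs no assumption.

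The numerical weight does rest on assumptions: the number of deaths, a two-sided exact interval and N=850. The case of eight failures plus one death is a boundary illustration, since 9/850 exceeds the limit by only 0.0004 percentage points. At the planned six failures, it takes three uncounted deaths to reverse the conclusion. The case for change is that the success rule omits the most serious failures, and not that a reversal is likely.

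**What to change.** 1. In 2.1, 3.4.1 and 4.1.1, add to the numerator: death within 30 days due to VTE or bleeding, or in which these cannot be excluded, regardless of hospital stay.
2. In 2.2, add a secondary endpoint with an exact 95% interval: any objectively confirmed recurrent VTE, major bleeding, or VTE- or bleeding-related death within 30 days, regardless of stay. Use this endpoint for comparison with the recurrence and major-bleeding rates in 1.1.
3. In 3.4, define a fatal VTE or bleeding event. In 3.3, provide record review for deaths that does not depend on the subject's own day-30 reply.

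The cost is modest but goes beyond wording. It needs a definition, a way to attribute cause of death and a small addition to follow-up procedures. VTE diagnoses, bleeding and re-hospitalizations are already asked about, and deaths are already collectable as serious adverse events. The reported failure rate may be slightly less favourable.
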